In patients with advanced stage non-small cell lung cancer who have received platinum doublet chemotherapy, the addition of plinabulin to nivolumab therapy will increase response rate compared to historical controls treated with nivolumab alone.

Objectives:

Primary Objective

- For the initial phase. To determine the safety and tolerability of the combination of nivolumab and plinabulin.
- For the subsequent phase. To determine the overall response rate (ORR) of treatment with nivolumab in combination with plinabulin for the treatment of advanced stage non-small cell lung cancer in the second line setting.

Secondary Objectives

- To determine the progression free survival (PFS), disease control rate (DCR), Duration of Response (DOR) and overall survival (OS) of patients treated with nivolumab in combination with plinabulin.
- To establish the safety and tolerability of nivolumab in combination with plinabulin.

Clinical trial design:

The trial will be conducted in two phases: the first phase will be a phase 1 dose-escalation to determine the safety of the combination and phase two will be an open label, phase II Simon Minimax 2-stage design of the combination of plinabulin and nivolumab in the treatment of patients with metastatic non-small cell lung cancer.

2.0 BACKGROUND

Lung cancer remains and most common cause of cancer death in both men and woman in the United States and worldwide. In 2015 it is estimated to cause 158,040 deaths in the United States.¹ The majority of these patients have non-small cell lung cancer, where despite advances in medical therapy, the response rate of patients treated with chemotherapy in the second line setting is below 10%. Recent studies have established that inhibition of the programmed death-1 (PD-1) checkpoint leads to a response rate of 15-20% in both squamous and non-squamous NSCLC. These results have led to a paradigm change, the FDA approved nivolumab for the treatment of metastatic squamous lung cancer and the National Comprehensive Cancer Network (NCCN) guidelines has recommended nivolumab as a second line therapy in all histologies. Although, undeniably, a great advance still the majority of patients do not respond to immune checkpoint inhibition and improving the response rate is of paramount importance.

With the hypothesis that treatment with a combination of plinabulin and nivolumab will increase the overall response rate of patients with metastatic non-small cell lung cancer compared to historical controls treated with nivolumab alone, we have designed the phase II study presented in this protocol.

Plinabulin

Plinabulin is a synthetic analog of the diketopiperazine phenylahistin discovered from an *Aspergillus* species. Plinabulin exerts its effect against cancer growth with several mechanisms. It inhibits Ras-JNK pathway and disrupts tubulin polymerization which causes direct cytotoxic action in a variety of cancer cell lines such as the human HT-29 (colon), PC 3 (prostate), MDA-MB-231 (breast), RPMI-8226 (multiple myeloma), and NCI-H292 (NSCLC) tumor cell lines.^{2, 3} It disrupts the cytoskeleton and tubulin network of endothelial cells, thereby inhibiting angiogenesis and causing vascular disruption and subsequent tumor cell death.^{2, 3}

A total of 141 patients with advanced cancers have received plinabulin in two clinical studies, a phase 1 monotherapy study and a phase 1/2 combination study with docetaxel.

As monotherapy plinabulin was generally well tolerated. Adverse events (AEs) that occurred in $\geq 20\%$ of patients included nausea (61%), vomiting (47%), diarrhea and fatigue (34% each), constipation, pyrexia, and headache (26% each), anorexia (24%), and anemia (21%). AE of all grades that were possibly related to plinabulin included nausea (53%), vomiting (37%), diarrhea (29%), and fatigue (21%). Overall, 16 (42%) patients experienced serious adverse events (SAEs), the majority of which were considered not related to plinabulin. No cardiac or neurologic side effects were observed. DLTs were not observed in patients treated at 30mg/m² in the dose-escalation portion of the study, however RP2D was determined to be 30 mg/m²

Clinical Study Protocol 9602
Drug Substance: plinabulin
IND: 129799
Protocol v5.1
Date 7/15/2017

based on mechanism-based adverse events and the presence of a biological response on tumor blood flow. While no patient achieved a CR or PR, the proportion of patients with stable disease appeared to increase with increasing plinabulin dose (7/18 (47%) evaluable patients achieved stable disease at the RP2D level).

In the phase 1/2, open label study to evaluate plinabulin in combination with docetaxel in patients with advanced NSCLC that had progressed after treatment with at least 1 chemotherapy regimen (2014 ASCO abstract. J Clin Oncol 32:5s, 2014 (suppl; abstr 8054). On the phase II portion of the study patients were randomized to receive plinabulin (30 mg on days 1 and 8) and docetaxel (75 mg on day 1) vs docetaxel alone. A total of 90 patients received plinabulin plus docetaxel and 73 received docetaxel alone. Plinabulin was found to be generally well tolerated in combination with docetaxel and appeared to have a similar AE profile as single agent docetaxel, although surprisingly the combination had a significantly lower rate of neutropenia (all events and events \geq Grade 3) than patients treated with docetaxel alone ($p \leq 0.01$). Furthermore, the proportion of patients who required G-CSF and the median cycles of G-CSF received, as well as the rate of docetaxel dose reduction, was lower with the combination than with docetaxel alone.

The most common AEs without regard to causality in the Phase 2 portion of the Phase 1/2 protocol at 30 mg/m² (RP2D) were diarrhea (58%), fatigue (52%), nausea (48%), constipation (36%), vomiting (34%), anorexia (34%), and transient hypertension (32%). Plinabulin did not cause a bleeding side effect, which is commonly seen with other anti-angiogenesis agents, such as bevacizumab or ramucirumab. There was no significant improvement in efficacy in patients who received plinabulin in addition to docetaxel, although the duration of response was significantly ($p < 0.05$) longer for those responded to plinabulin 30 mg/m² plus docetaxel (12.7 months) than docetaxel alone (1.5 months).

Nivolumab

Nivolumab is a fully human IgG4 programmed death 1 (PD-1) immune-checkpoint-inhibitor antibody. CheckMate-017 was a randomized phase III trial that randomly assigned 272 patients with metastatic squamous lung cancer to receive nivolumab, at a dose of 3 mg per kilogram of body weight every 2 weeks, or docetaxel, at a dose of 75 mg per square meter of body-surface area every 3 weeks. Overall survival for patients treated with nivolumab was 9.2 months compared to 6 months in patients treated with docetaxel alone (HR, 0.59; 95% CI, 0.44 to 0.79; $P < 0.001$). The response rate was 20% with nivolumab versus 9% with docetaxel ($P = 0.008$). These results led to the approval of nivolumab for the patients with metastatic squamous lung cancer.⁴

CheckMate-057 used the same study design but focused on patients with non-squamous lung cancer, here OS was also improved for patients treated with nivolumab compared to those treated with docetaxel (12.2 months vs. 9.4 months, HR= 0.73; 95% CI, 0.59 to 0.89; p=0.0012). The NCCN guideline has recommended consideration for this agent in the second line setting and it has been granted approval by the FDA for patients who have progressed through a first line platinum doublet chemotherapy.

Nivolumab treatment is well tolerated with a low incidence of severe adverse events. In CheckMate 017 treatment-related adverse events of grade 3 or 4 were reported in 7% of the patients in the nivolumab group as compared with 55% of those in the docetaxel group. The most common side effects seen with nivolumab are fatigue (16%), decreased appetite (11%), asthenia (10%), nausea (9%), diarrhea (8%), arthralgia (5%), pyrexia (5%) and pneumonitis (5%).⁴

Microtubule depolymerizing agents as immunomodulators.

Microtubule depolymerizing agents (MDA) have been shown to promote dendritic cell maturation⁵⁻⁷. Ansamitocin P3 is a MDA that induces DC maturation, production of pro-inflammatory cytokines and when used in combination with immune checkpoint inhibitors, potentiated the antibody-mediated blockade and produced a more pronounced anti-tumor effect in a colon cancer murine model.⁵ Dolastatin, another animal derived MDA, has been shown in murine models to promote antigen uptake and migration of tumor-resident DCs to tumor draining lymph nodes. In the same models, blockade of the PD-1 pathway induces therapeutic synergy when combined with dolastatin. Brentuximab vedotin, an antigen drug conjugate, that uses an antimetabolic agent monomethyl auristatin E as its chemotherapy partner has been shown to induce dendritic cell homing and activation of the cellular antitumor immune responses in patients.⁷ Plinabulin has been shown to have activity in inducing DC maturation in a dose dependent manner, similar to that of Ansamitocin P3 (unpublished data). Plinabulin has also been shown in an immune-competent mice model MC38 model that it adds efficacy synergy in tumor inhibition of PD-1 antibody in a statistically significant manner (unpublished data).

3.0 TRIAL OBJECTIVES

Primary Objective.

- For the initial phase. To determine the safety and tolerability of the combination of nivolumab and plinabulin.
- For the subsequent phase. To determine the overall response rate (ORR) of treatment with nivolumab with the addition of plinabulin in the treatment of advanced stage non-small cell lung cancer in the second line setting.

Secondary Objectives.

- To determine the progression free survival (PFS), disease control rate (DCR), Duration of Response (DOR) and overall survival (OS) of patients treated with nivolumab in combination with plinabulin.
- To determine the safety and tolerability of the combination of plinabulin and nivolumab.

Translational objectives.

- Patients who have pre-treatment and/or post cycle one biopsy will have flow cytometry of their tissue to identify infiltration of immune cells, rates of expression of PD-1, PD-2 and PDL1. In partnership with [name], we will correlate the percentage and characteristics of immune cells with response to therapy.

4.0 STUDY POPULATION AND SELECTION OF SUBJECTS.

Inclusion criteria

Patients must meet the following criteria to be eligible to participate in the current study:

1. Subjects must have histologically or cytologically-documented stage IIIB or stage IV, recurrent, or metastatic NSCLC.
2. Subjects must have received prior platinum doublet based treatment.
 - Up to 2 lines of prior systemic therapy for metastatic disease are permitted.
 - Adjuvant chemotherapy or concurrent chemoradiation for early stage disease does not count as prior therapy unless subject progressed within 6 months of completion of regimen
 - Patients with known activating mutations in EGFR, or known translocation in ALK or ROS-1 are eligible provided they have progressed on or were intolerant to FDA approved targeted therapy.
3. Subjects must be ≥ 18 years of age.
4. Subjects must have an Eastern Cooperative Oncology Group (ECOG) performance status of 0 to 2.
5. Subjects, including those in the dose-escalation portion of the study, must have measurable disease per RECIST 1.1 criteria. Imaging must be within 28 days of trial enrollment.
 - Target Lesions may be located in a previously irradiated field if there is documented (radiographic) disease progression in that site prior to trial enrollment
6. Subjects must have organ and marrow function as follows:
 - Absolute neutrophil count (ANC) $\geq 1000/\text{mm}^3$,

- Platelets $\geq 75,000/\text{dL}$,
 - Hemoglobin $\geq 9 \text{ g/dL}$,
 - Total bilirubin $\leq 1.5 \times \text{ULN}$ (except subjects with Gilbert Syndrome who can have total bilirubin $\leq 3.0 \text{ mg/dL}$),
 - Serum creatinine $\leq 1.5 \text{ mg/dL}$ or creatinine clearance $\geq 60 \text{ mL/min}$,
 - Alanine aminotransferase (ALT) and aspartate aminotransferase (AST) ≤ 2.5 times the upper limit of normal if no liver involvement or ≤ 5 times the upper limit of normal with liver involvement
7. For women of child bearing potential, documented negative pregnancy test within two weeks of study entry and agreement to acceptable birth control throughout the trial starting with the screening visit through 120 days after the last dose of study medication
 - Abstinence is an acceptable method of birth control
 8. Male subjects with a female partner(s) of child-bearing potential must agree to use acceptable birth control throughout the trial starting with the screening visit through 120 days after the last dose of study medication.
 9. Capability to understand and comply with the protocol requirements as and signed informed consent documents.

Exclusion criteria

1. Systemic anticancer therapy within 21 days of the first dose of study drug.
 - All adverse events from prior systemic therapy must have either stabilized or returned to baseline.
2. Prior treatment with nivolumab or any other PD1/PDL1 checkpoint inhibitor.
3. Major medical conditions that might affect study participation (e.g. uncontrolled pulmonary, renal, or hepatic dysfunction, uncontrolled serious infection, cardiac disease).
4. Significant cardiac history:
 - History of myocardial infarction or ischemic heart disease within 1 year before first study drug administration;
 - Uncontrolled arrhythmia;
 - History of congenital QT prolongation;
 - New York Heart Association Class III or IV cardiac disease;
 - Uncontrolled hypertension: blood pressure consistently greater than 150 mm Hg systolic and 100 mm Hg diastolic in spite of antihypertensive medication.
5. History of hemorrhagic diarrhea, inflammatory bowel disease or active uncontrolled peptic ulcer disease. (Concomitant therapy with ranitidine or its equivalent and/or omeprazole or its equivalent is acceptable). History of ileus or other significant gastrointestinal disorder known to predispose to ileus or chronic bowel hypomotility.

6. Subjects with untreated symptomatic CNS metastases are excluded.
 - Subjects are eligible if symptomatic CNS metastases are treated and subjects have neurologically returned to baseline (except for residual signs and symptoms related to CNS treatment) for at least 7 days prior to first dose of study treatment.
 - Subjects must be off corticosteroids for at least 7 days prior to first dose of study treatment.
7. Subjects with leptomeningeal disease are excluded.
8. Subjects with planned radiation therapy to a target lesion will be excluded.
9. Radiation therapy within 14 days of the first dose of study drug.
10. Subjects who are pregnant or breastfeeding are excluded.
11. Subjects who are unable or unwilling to abide by the study protocol or cooperate fully with the investigator or designee are excluded.
12. Pulmonary conditions such as sarcoidosis, silicosis, idiopathic pulmonary fibrosis, or hypersensitivity pneumonitis are excluded.
13. Subject who have active non-infectious pneumonitis.
14. Subjects who have a diagnosis of immunodeficiency or are receiving systemic steroid therapy or any other form of immunosuppressive therapy within 7 days prior to the first dose of study treatment.
15. Subjects with any active, known, or suspected autoimmune disease. Subjects with type I diabetes mellitus, hypothyroidism only requiring hormone replacement, skin disorders (such as vitiligo, psoriasis, or alopecia) not requiring systemic treatment, or conditions not expected to recur in the absence of an external trigger are permitted to enroll.
 - Subjects with asthma that require intermittent use of bronchodilators, inhaled steroids, or local steroid injections would not be excluded from the study.
 - Subjects on chronic systemic steroids for any reason would be excluded from the study. The use of topical steroids is allowable.
16. Any known additional malignancy (with exception of non-melanoma skin cancer, in-situ breast cancer or a malignancy diagnosed ≥ 3 years ago and with no evidence of requiring active treatment).
17. Patients with known active Hepatitis B, or Hepatitis C will be excluded.
18. Patients with risk factors for bowel obstruction or bowel perforation (e.g., acute diverticulitis) will be excluded.
19. Has any serious or uncontrolled active infection.

5.0 TRIAL DESIGN AND TREATMENT PLAN.

Trial design

The trial will be conducted in two phases an initial phase 1 portion and a subsequent phase 2 portion which will be a single center, two stage Simon,

phase 2 open label study of patients with advanced stage lung cancer treated in the second or third line setting with plinabulin and nivolumab.

Endpoints

5.1.1 Primary endpoints.

- For the initial phase. To determine the safety and tolerability of the combination of nivolumab and plinabulin.
- For the subsequent phase, To evaluate the overall response rate, defined as the sum of complete and partial responses according to RECIST 1.1 criteria, of patients treated with a combination of plinabulin and nivolumab.

5.1.2 Secondary endpoints.

- Evaluate disease control rate, defined as the proportion of patients with CR, PR and SD for more than 8 weeks while on combination plinabulin and nivolumab.
- Evaluate duration of response (DOR), Progression Free Survival (PFS) and Overall Survival (OS)
- Determine the safety and tolerability of the combination of nivolumab and plinabulin.

Dose rationale

Plinabulin has been studied as a single agent in a dose escalation study, the maximum tolerated dose was not reached and the recommended phase 2 dose was 30mg/m². A subsequent phase 1 study using plinabulin with docetaxel showed that plinabulin did not contribute to the toxicity of docetaxel⁹. In this study the initial phase will start with a dose of plinabulin of 20 mg/m² and nivolumab at a flat dose of 240mg. If no dose limiting toxicities (DLTs) are seen the dose of plinabulin will be escalated to 30 mg/m²

Treatment plan

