5.1.4 Second Phase

In the second phase of the study patients will receive plinabulin at the MTD identified previously and nivolumab 240 mg on the same day and repeated every 2 weeks. Re-staging studies will be conducted every 8 (+/-1) weeks, after cycle seven scans will be done every 12 (+/-1) weeks. Those who achieve a complete response, partial response, or stable disease will continue on study. Will use RECIST 1.1 criteria to determine response to treatment. Patients with progressive symptomatology and progressive disease seen in imaging studies will be taken off study. To account for pseudo-progression, in the case of progressive disease in the absence of worsening symptomatology, at the discretion of the treating physician, a patient will be allowed to continue receiving treatment for 2 more cycles followed by restaging studies. If progressive disease is confirmed the patient will be taken off study.

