6.6 Tumor Evaluations

CT scan of all known areas of disease with tumor evaluation using RECIST 1.1 and IrRC criteria will be performed every 8 (+/-1) weeks. After 7 cycles of therapy, imaging studies will be performed every 12 (+/- 1) weeks.

- Patients who have a CR, PR, or SD may continue on study per study protocol.
- If progressive disease is documented the patient may remain on study provided:
 - The patient does not have clinical signs or symptoms of tumor progression
 - No decline in ECOG performance status
 - Absence of progressive tumor at critical anatomic sites (i.e. spinal cord compression).
 - Treating physician believes that the patient continues to derive clinical benefit from study treatment
 - Repeat imaging scans should be repeated ≥ 4 weeks (+/- 7 days) after documented progression. If progression is confirmed the subject will be removed from study.

Off Study Visit.

Patients will undergo the following assessments 28 days (+/- 14 days) after last dose of study treatment

- History and physical examination that includes examination of major organ systems, ECOG performance status, weight, vital signs, adverse events assessment
- Laboratory evaluations including:
 - CBC with differential
 - Blood chemistry (sodium, potassium, chloride, carbon dioxide, creatinine, BUN, glucose, calcium, albumin, bilirubin, AST, ALT, total protein, and alkaline phosphatase)

Permitted medications

All treatments that the investigator considers necessary for a subject's welfare may be administered at the discretion of the

investigator in keeping with the community standards of medical care.

If an increase in systolic blood pressure to > 160 mmHg is observed after administration of plinabulin, oral amlodipine 10 mg or an equivalent calcium channel blocker should be administered before each subsequent dose. Increases in systolic blood pressure above 200 mmHg should be managed with nitroprusside or similar regimen per institutional practice.

Dexamethasone may be used as either a pre-medication or as a rescue medication for patients that experience plinabulin-related nausea and vomiting that is not controlled adequately with a 5HT3 agonist (e.g. ondansetron) alone

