8.3 Data and Safety Monitoring Plan

The PI of the study will have primary responsibility for ensuring that the protocol is conducted as approved by the FHCRC/UW Cancer Consortium Scientific Review Committee and Institutional Review Board. The PI will ensure that the monitoring plan is followed, that all data required for oversight

of monitoring are accurately reported to the FHCRC/UW Cancer Consortium Data and Safety Monitoring Committee (DSMC), that all adverse events are reported according to the protocol guidelines, and that any adverse reactions reflecting patient safety concerns are appropriately reported.

Under the provisions of the FHCRC/UW Cancer Consortium Data and Safety Monitoring Plan (DSMP), Cancer Consortium Clinical Research Support (CRS) provides monitoring for quality process and compliance by qualified monitors unaffiliated with the conduct of the study. Monitoring visits occur at specified intervals determined by the assessed risk level of the study and the findings of the previous visit as described in the Cancer Consortium DSMP.

9.0 STATISTICAL METHODS AND DATA ANALYSIS.

- 9.1 Sample size determination for the second phase of the study.
For all patients treated at a dose of plinabulin of 30 mg/m² or at the MTD the study will follow a Simon 2 two-stage Minimax design.¹⁰ The null hypothesis that the true response rate is 20% will be tested against the one-sided alternative of a response rate of more than 40%. In the first stage, once 18 patients are accrued the study will stop. If there are 4 or fewer responses in these 18 patients, the study will be terminated. Otherwise the study will reopen and 15 additional patients will be accrued. The null hypothesis will be rejected if 11 or more responses are observed in these evaluable 33 patients. This design yields a type I error rate of .05 and a power of 0.8 when the true response rate is 40%. If the true response rate is 20% the probability of ending the trial during the first stage is 0.72. If the true response is 0.4 the probability that the trial will be stopped in the first stage is 0.09. During the initial phase 1 portion of the study 3 or 6 patients will be enrolled for a total sample size of 39 patients.

- 9.2 Efficacy Analysis.

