The study population for analyses will include all patients enrolled in the study who receive treatment at the MTD and receive at least one dose of study medication. The primary endpoint will be overall response rate. As noted above, 11 or more observed responses among 33 patients would be considered potentially efficacious and would justify further study. Responses include both complete and partial responses, as defined by RECIST 1.1 criteria. The disease control rate (DCR), defined as the stable disease + partial response rate will be calculated. Toxicity rates will be described as the overall percentage of patients experiencing Grade 3 or higher toxicity.

9.3 Time to event definitions.

Progression free survival is defined as the time from registration until objective tumor progression or death due to any cause, whichever comes first. The date of disease progression will be defined as the earliest date of radiological disease progression as assessed by the investigator using RECIST 1.1 criteria, or clinical disease progression. For patients who have not progressed or died at the time of the analysis, censoring will be performed using the date of the last adequate disease assessment.

Overall survival is defined as the time from registration until the date of death due to any cause. Patients last known to be alive at the time of the analysis will be censored at the date of last contact.

Duration of response is defined as the time between receipt of first study drug and until the date of progression.

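### DCR is defined in two incompatible ways, and the Section 5.1.2 version sets its 8-week SD minimum in the middle of the first-scan window

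*Combined protocol and SAP*

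**What the plan says.** The combined protocol and SAP defines DCR in two places.

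- Section 5.1.2 (secondary endpoints): "defined as the proportion of patients with CR, PR and SD for more than 8 weeks while on combination plinabulin and nivolumab". CR is included, SD has a minimum duration, and the status must hold on the combination. I read the minimum as applying to SD only.
- Section 9.2 (efficacy analysis): "The disease control rate (DCR), defined as the stable disease + partial response rate will be calculated". There is no minimum duration, no on-combination condition, and CR is not named.

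The scan schedule is the same throughout. Section 5.1.4 says "Re-staging studies will be conducted every 8 (+/-1) weeks, after cycle seven scans will be done every 12 (+/-1) weeks", Section 6.6 repeats the interval ("using RECIST 1.1 and IrRC criteria will be performed every 8 (+/-1) weeks"), and the schedule of events agrees. No earlier post-baseline scan is planned.

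Section 9.3 gives time origins for other endpoints. For PFS: "Progression free survival is defined as the time from registration until objective tumor progression or death due to any cause". OS also starts at registration; duration of response starts at first study drug and runs to progression. For SD, the plan gives neither a starting point nor an end point.

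**The concern.** Two definitions of one named endpoint leave the analyst to choose. A complete responder counts under Section 5.1.2 but not under the letter of Section 9.2. A patient with brief SD counts under Section 9.2 but may not under Section 5.1.2.

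Within Section 5.1.2, the minimum and the scan window also fit badly. A first scan exactly on schedule at week 8 cannot, by itself, document SD of more than 8 weeks, while a scan a day later can. Two patients with the same course, both managed within protocol, could then be classified differently because of an appointment date. At stake is the interpretability of a secondary endpoint in a small single-arm trial, where each patient moves the rate noticeably.

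**Working it through.** The plan states no expected DCR, sample size or test for it, so there is no figure to reproduce. The check compares days, then scales the result.

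**Inputs.** Scan interval 8 weeks with a window of 1 week either side (Sections 5.1.4 and 6.6). SD minimum strictly more than 8 weeks (Section 5.1.2). N = 33, from Section 9.1: "The null hypothesis will be rejected if 11 or more responses are observed in these evaluable 33 patients". Assumptions: scan days and SD duration are both counted in days elapsed from first dose, SD ends at the last scan showing it, and the DCR denominator is 33.

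**Step 1, first-scan window.** 8 × 7 = 56 days; 56 ± 7 gives days 49 to 63, which is 63 − 49 + 1 = 15 permitted days.

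**Step 2, days on which SD at the first scan qualifies.**

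| SD minimum | Qualifying days | Failing days |
|---|---|---|
| more than 56 days (Section 5.1.2) | 57–63: 7 of 15 (47%) | 49–56: 8 of 15 (53%) |
| at least 56 days | 56–63: 8 of 15 | 49–55: 7 of 15 |
| at least 49 days | 49–63: 15 of 15 | none |

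Replacing the strict inequality with 'at least 8 weeks' rescues the on-schedule scan but still splits the window.

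**Step 3, sensitivity to the origin.** If the clock started at registration, k days before first dose, a scan on day d would qualify when d + k > 56. With k = 8, day 49 gives 57, so all 15 days qualify. The 7-to-8 split therefore depends on the first-dose origin.

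**Step 4, who is affected.** The second scan is due at about 16 × 7 = 112 days, window 105 to 119. Four patients, all with SD at the first scan:

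| Course | 5.1.2, SD timed to last SD scan | 5.1.2, SD timed to progression | 9.2 |
|---|---|---|---|
| SD day 50, PD about day 112 | no | yes | yes |
| SD day 60, PD about day 112 | yes | yes | yes |
| SD day 50, leaves without progression, no later scan | no | not stated | yes |
| SD day 60, leaves without progression, no later scan | yes | yes | yes |

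Patients with CR or PR, and those still free of progression at the second scan, are unaffected by the first-scan day under Section 5.1.2.

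**Step 5, size.** One patient is 1/33 = 3.0 percentage points. The number affected is not in the documents.

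**The case against.** The strongest answer is that SD is described as a duration, and the plan's other disease-status durations run to progression. On that reading, SD on day 50 with progression near day 112 lasted well over 8 weeks, and the first-scan day does not matter. Section 9.3 also accepts clinical progression as an end date, so what remains is mainly patients who leave without progression or death. This is a fair reading, but the plan does not state it, and it leaves those remaining patients unclassified.

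Second, Section 9.2 is the analysis text and has no minimum, so under it the window problem does not arise. That is true. The cost is that Section 5.1.2 is then not followed and CR is left out.

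Third, the schedule of events marks a CT at the off-study visit. A last dose on Cycle 2 Day 15 is 28 + 14 = 42 days after first dose, so the visit falls at 42 + 28 = 70 days. With the 14-day window in the off-study text this is 56 to 84 days; with the 7-day window in the schedule footnote it is 63 to 77. Nearly all of these days exceed 56, so such a scan could rescue some patients. But the off-study text does not list a CT, and a scan after the last dose may not count as being on the combination.

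Two stronger readings are tempting. A reader might infer a swing of 9 to 24 points, from 3 to 8 affected patients (3/33 = 9.1%, 8/33 = 24.2%). Those counts are assumed, and the swing compares every such patient scanned early with every one scanned late. With scan days spread evenly, the loss would be 8/15 of that, about 5 to 13 points, and only if SD is timed to the last SD scan. A reader might also infer that an open-label site could steer the result through scan dates. The documents do not support this: the finding is unknown when the scan is booked.

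**Conclusion.** The conflict between Sections 5.1.2 and 9.2 is plain on the text and needs no assumption. The scan-day dependence is real but conditional. It requires that Section 5.1.2 governs, that SD is timed from first dose, and that it ends at the last SD scan; it then touches only patients with no later assessment free of progression. Under those conditions an in-window first scan showing SD fails on 8 of 15 permitted days, including the scheduled one. Under other defensible readings the effect is smaller or absent.

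No total effect on DCR can be stated beyond about 3 points per affected patient at N = 33. DCR is secondary and descriptive, and the decision rule counts responses only, so the primary ORR conclusion does not change. This is a definition to settle before analysis, not a flaw in the trial's main inference.

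**What to change.** Put one definition in both Section 5.1.2 and Section 9.2: DCR is the proportion of patients with CR, PR, or SD, where SD must be documented on a scan at least 7 weeks (49 days) after first dose. Any in-window first scan showing SD then qualifies. State first dose as the time origin explicitly, since PFS and OS start at registration, and say whether the on-combination condition is kept.

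Record actual scan days, and report a sensitivity count requiring absence of progression at the second scan (about weeks 15 to 17), so that the stricter view is visible.

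Timing SD to progression would be an alternative, but it would still need a rule for patients who leave without progression and without a later scan. The 49-day minimum avoids that for anyone scanned in the window.

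The cost is a wording change in two sections and one extra tabulation, with no added visits or scans. The SD cut-off becomes up to one week less strict.
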